The RCC-PI will review all data including medical records, death certificates, data provided by the parent/legal guardian, and any follow-up confirmatory data provided by HCPs. The RCC-PI may request targeted follow-up data from the relevant HCP or medical facility if clarification is needed on any reported study endpoints or SAEs.

When a congenital anomaly is reported, it will be reviewed by an expert in teratology who is engaged by the RCC-PI to serve as the birth defect evaluator for this study. The birth defect evaluator's responsibilities will include the review, evaluation, and classification of all reports of birth defects.

To screen for developmental issues, the parent/legal guardian will be asked to complete the 9-, 18-, and 24-month ASQ-3 when the infant's corrected age corresponds to 9, 18, and 24 months, for example, parents/legal guardians of an infant born 3 months premature will complete the 9-month ASQ-3 at 12 months chronological age. Any child

who scores in the black zone (≥ 2 SD below the mean) (see Section 6.2.5.1) in any of the 5 domains of the ASQ-3 will be referred to a qualified assessor for a developmental evaluation (e.g., using the Bayley Scales of Infant Development, third edition [BSID-III]), and a neurologic examination will be conducted, if indicated. An overall assessment of delay in the areas of communication, gross and fine motor, problem-solving, and personal-social development will be rendered. As part of normal management, some infants may already have undergone a formal developmental evaluation using the BSID-III; in these cases, if testing was recent (≤ 3 months), the BSID-III will not be repeated and RCC-PI will request results from the relevant HCP. BSID-III retesting will be requested if the child's ASQ-3 scores are in the black zone on a subsequent ASQ-3 test following the first BSID III referral. Based on results from the ASQ-3 administered at 24 months corrected age and if no cerebral palsy diagnosis has been made to date (see Section 6.2.5.1), the infant may be referred to a qualified examiner for a formal assessment of cerebral palsy.

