6.2.1.1. Confirmation of Parent-Reported Data

If the parent/legal guardian indicates that the child has been newly diagnosed (after 28 days post EDD) with chronic conditions or congenital anomalies via the CHI, follow-up will be undertaken via the RCC-PI with the applicable HCP to confirm the parent report. At subsequent CHIs, if the parent/legal guardian indicates that a previously reported condition has worsened or resolved, the HCP will also be asked to provide confirmation. If the condition qualifies as an SAE, additional information will be requested to assist the RCC-PI with the process of SAE reporting.

The specific process by which confirmation with HCPs and health care facilities will be obtained is presented in the SPM.

All morbidity and mortality endpoints (defined in Section 6.2) will require medical confirmation. All hospitalizations and deaths require medical confirmation by medical records or death certificate. All surgeries, except routine, simple outpatient procedures (e.g., circumcision), require confirmation by medical records. If the parent/legal guardian indicates that the child has had an ER/UC visit, the RCC-PI will use discretion and obtain medical records when the reported indication suggests a true emergency. Additional details regarding ER/UC visits will be provided in the SPM. If follow-up with the HCP is recommended, medical confirmation of the follow-up is required.

The confirmation process is iterative and may be triggered at multiple times throughout the study to provide confirmation of parent-reported conditions and events. Medical input will override parent-reported data. An overview for the collection and review of data for the CHI is provided in [Figure 2](#).

Figure 2 Child Health Inventory: Flow Chart of Data Collection and Review

CHI = Child Health Inventory; HCP = health care provider; RCC-PI = research coordinating center-principal investigator.

1. The CHI completed at 2, 6, 9, 12, 15, 18, 21, and 24 months of the child's chronological age will screen for infant mortality and morbidity and capture data on resource utilization.

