6.2.5.1. The ASQ-3 Score Interpretation and Possible Specialist Referral Recommendations

The ASQ-3 scores for this study will be interpreted and recommendations will be offered according to the following:

[figure not shown]
- The child’s development will be considered to be on schedule if the child’s ASQ-3 scores are in the white zone (higher than 1 SD below the mean), and no further action is required.
- If the child’s ASQ-3 scores are in the grey zone (≤ 1 SD below the mean), the parent/legal guardian may share the ASQ-3 test results with the child’s HCP.

- If any of the child's ASQ-3 scores are in the black zone (≥ 2 SD below the mean), then the child's parent/legal guardian will be asked if the child is already under the care of a developmental specialist who can or has made a formal assessment (e.g., using the BSID-III). If a recent (≤ 3 months) BSID-III was conducted, the BSID-III will not be repeated and the RCC-PI will request results from the relevant HCP. If the child is not currently under the care of a developmental specialist, then the parent/legal guardian will be referred to a qualified assessor for developmental evaluation (e.g., using the BSID-III), and a neurologic examination will be conducted, if indicated.
- BSID-III retesting will be performed if the child's ASQ-3 scores are in the black zone on a subsequent ASQ-3 test following the first BSID-III referral.
- If, at 24 months corrected age, the child's ASQ-3 gross motor domain score is in the black range and the child has not already been diagnosed with cerebral palsy, the parent/legal guardian will be referred to a qualified examiner for a formal assessment to determine if this condition is present.

Reports from all specialists will be included in the subject's source documents. For further details regarding the ASQ-3 refer to the SPM.

An overview for the collection and review of data for the ASQ-3 is provided in [Figure 3](#).

Figure 3 ASQ-3, M-CHAT-R/F, and CBCL/1.5–5: Flow Chart of Data Collection and Review

ASQ-3 = Ages and Stages Questionnaire-3; BSID-III = Bayley Scales of Infant Development, third edition; CBCL/1.5–5 = Child Behavior Checklist for ages 1.5 to 5; HCP = health care provider; M-CHAT-R/F = Modified Checklist for Autism in Toddlers-Revised with Follow-Up; RCC-PI = research coordinating center-principal investigator.

1. A neurologic examination will also be conducted, if indicated.

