6.2.6. Overall Measure of Neurodevelopmental Impairment

- Proportion of infants with at least 1 of the following indicators of neurodevelopmental impairment:
 - Hearing impaired, uncorrected even with aids (at 24 months chronological age)
 - Blindness in 1 or both eyes, or sees light only (at 24 months chronological age)
 - Cerebral palsy (moderate defined as grade 2 or 3 and severe defined as grade 4 or 5 using the Gross Motor Functional Classification System [GMFCS]) (at 24 months corrected age)

- Cognitive impairment: BSID-III Cognitive Scale Score of >2 SDs below mean score (<4) (at 24 months corrected age)
- Motor impairment: BSID-III Motor Composite Scale Score of >2 SDs below mean score (<70) (at 24 months corrected age)
- Diagnosis of ASD, ADD, or ADHD

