To screen for developmental issues, the parent/legal guardian will be asked to complete the 9-, 18-, and 24-month ASQ-3 when the infant's corrected age corresponds to 9, 18, and 24 months, for example, parents/legal guardians of an infant born 3 months premature will complete the 9-month ASQ-3 at 12 months chronological age. Any child who scores in the black zone (≤ 2 SD below the mean) (see Section 6.2.5.1) in any of the 5 domains of the ASQ-3 will be referred to a qualified assessor for a developmental evaluation (e.g., using the Bayley Scales of Infant Development, third edition [BSID-III]), and a neurologic examination will be conducted, if indicated. An overall assessment of delay in the areas of communication, gross and fine motor, problem-solving, and personal-social development will be rendered. As part of normal management, some infants may already have undergone a formal developmental evaluation using the BSID-III; in these cases, if testing was recent (≤ 3 months), the BSID-III will not be repeated and RCC-PI will request results from the relevant HCP. BSID-III retesting will be requested if the child's ASQ-3 scores are in the black zone on a subsequent ASQ-3 test following the first BSID III referral. Based on results from the ASQ-3 administered at 24 months corrected age, ~~parents/legal guardians may be asked to complete the Child Behavior Checklist for Ages 1.5 to 5 (CBCL/1.5-5) and the Modified Checklist for Autism in Toddlers Revised with Follow-Up (M-CHAT-R/F) to assess the risk for other behavioral problems or autism spectrum disorder or, alternatively, and if no cerebral palsy diagnosis has been made to date~~, the infant may be referred to a qualified examiner for a formal assessment of cerebral palsy.

The Modified Checklist for Autism in Toddlers–Revised with Follow-Up (M-CHAT-R/F) will be completed for all infants at 18 and 24 months (corrected age) and the Child Behavior Checklist for Ages 1.5 to 5 (CBCL/1.5–5) will be completed for all infants at 24 months (corrected age) to assess the risk for other behavioral problems or autism spectrum disorder (ASD). If at any of these time points a child has an M-CHAT-R/F score that indicates further evaluation is required and/or a CBCL/1.5–5 score at or above the 97th percentile for a subset of prespecified questions, the child will be referred to a specialist for a formal assessment.

Section 3.2., Discussion of Design

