### **7.2.5. Neurodevelopment Impairment at the End of Study**

Number of infants and percentage of neurodevelopment impairment endpoints and individual components will be summarized at the end of study (24 months). Individual components at the end of study are listed in Section 2.2.

Motor composite score will be derived from fine motor and gross motor scaled scores in a similar fashion to language composite score described in Section 7.2.3

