### 10.6.2. Handling of Missing Data

Element	Reporting Detail
General	

• Missing data occurs when any requested data is not provided, leading to blank fields on the collection instrument :

[1] These data will be indicated by the use of a “blank” in subject listing displays.

[2] Answers such as “Not applicable” and “Not evaluable” are not considered to be missing data and should be displayed as such.

• For disposition and demographic data, no imputation will be done.

• For safety and neurodevelopment data, it will be assumed that the events of interest did not occur.

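### A child with an earlier low BSID-III and no 24-month retest is, on a literal reading of the SAP, counted as not impaired on the composite's cognitive and motor components

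*Protocol*

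**What the plan says.** **When BSID-III is repeated.** Protocol 3.1 makes a repeat depend on the parent questionnaire: "BSID-III retesting will be requested if the child's ASQ-3 scores are in the black zone on a subsequent ASQ-3 test" after the first referral. Protocol 6.2.5.1 has the same rule: "BSID-III retesting will be performed if the child's ASQ-3 scores are in the black zone on a subsequent ASQ-3 test". The sentence also stands in the Appendix 1 amendment log, but the current text in 3.1 and 6.2.5.1 is what counts. Where a recent (3 months or less) "BSID-III was conducted, the BSID-III will not be repeated and the RCC-PI will request results from the relevant HCP".

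**What the composite uses.** Protocol 6.2.6 lists six indicators, any one of which makes the child impaired. Two come from BSID-III, and both are dated. The motor one reads "Motor impairment: BSID-III Motor Composite Scale Score of >2 SDs below mean score (<70) (at 24 months corrected age"; the cognitive one (<4) carries the same timing. SAP 2.2 repeats both.

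**How it is summarised.** SAP 7.2.5 says the composite and its "individual components will be summarized at the end of study (24 months"). SAP 7.2 has every summary table carry N, the number of subjects in the treatment group. SAP 10.6.2 adds: "For safety and neurodevelopment data, it will be assumed that the events of interest did not occur".

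**What is not said.** Neither document gives an analysis window for BSID-III (the stated windows cover the questionnaires only). Neither says whether a BSID-III from the 9- or 18-month evaluation can enter the 24-month composite.

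**The concern.** The composite is meant to say how many children are impaired at 24 months. For its two BSID-III components, a 24-month score exists only if the 24-month ASQ-3 was returned, was in the black zone, and led to a test (or to a recent result being used). A child whose cognitive or motor score was already below the cut-off at 9 or 18 months can fail any of these conditions. Nothing then shows that the child recovered, yet the full-group N and the no-event rule produce a 'no'.

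Among these children the error runs one way: it can only lower the number counted as impaired. The study's stated goal (Protocol 1.2) is to give assurance about adverse outcomes in early childhood, so an undercount of impairment is the direction that matters. Protocol 3.2 also warns that loss to follow-up can bias ascertainment. A reader of Table 10.9 who sees fewer impaired children than Table 10.7 implies could not tell recovery from absence of a retest.

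**Working it through.** The plan states no figure for this point, so there is no result of its own to reproduce. Two adjacent figures were checked, and both agree.

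- Cut-offs, from the metrics in SAP 7.2.3: scaled score 10 − 2×3 = 4; composite score 100 − 2×15 = 70. These match <4 and <70.
- Enrolment, from the Amendment 2 justification in Protocol Appendix 1: 49 + 43 + 6 = 98, and 98/1230 = 8.0%, the stated 8%.

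**Scoring path.** Take a child with an 18-month ASQ-3 in the black zone and a BSID-III cognitive score of 3 at 19 months.

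1. 24-month ASQ-3 black and retest done: a 24-month score exists and the component is scored on it. No problem.
2. ASQ-3 black, retest requested but not done: requested data are absent, so SAP 10.6.2 gives 'no'.
3. ASQ-3 not returned: requested data are absent and no retest is triggered, so again 'no'.
4. ASQ-3 returned in the grey or white zone: no retest is requested. SAP 10.6.2 defines missing data as requested data not provided, so it does not clearly apply. The child still stays in N without a 24-month score to enter the numerator, and the effect is the same.

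In routes 2 to 4 the child is unimpaired in Tables 10.9 and 20.9 unless hearing, vision, moderate or severe cerebral palsy, or an ASD/ADD/ADHD diagnosis makes the composite positive.

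**Weight of one child** (1/n):

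| Group | ARIOS Safety | Infant Safety* |
|---|---|---|
| Retosiban | 1/49 = 2.0 points | 1/60 = 1.7 |
| Atosiban | 1/43 = 2.3 | 1/47 = 2.1 |
| Placebo | 1/6 = 16.7 | 1/13 = 7.7 |
| All comparators | 1/49 = 2.0 | 1/60 = 1.7 |

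*Assumes that all treatment-study participants reported in Protocol 1.1.1 were dosed and count: retosiban 10 + 50 = 60, atosiban 47, placebo 13.

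**Illustration only; neither input is in the documents.** Let k be the number of earlier positives in an arm and s the chance that a 24-month score is obtained. The expected number without one is k(1 − s), and the chance of at least one is 1 − s^k.

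- k = 1, s = 0.9: 1 × 0.1 = 0.1 children; chance 0.10.
- k = 5, s = 0.5: 5 × 0.5 = 2.5 children; chance 1 − 0.5^5 = 0.97.
- s = 1: zero.

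Here s combines routes 2 to 4, so only part of any loss comes from the retest trigger; the rest is ordinary missing data. Some of the children not retested will also have caught up.

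**The case against.** The strongest reply is that the scoring is inferred. The SAP never says an earlier BSID-III is ignored. SAP 3 leaves derivations to the ADaM specification, and Appendix 8 leaves table shells to a separate document; either may settle it. That stands: the defect is an undefined derivation whose literal reading drops these children, not an explicit instruction to drop them.

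A second reply is that an age-specific endpoint is legitimate and an early low score may normalise by 24 months. That also stands. Not carrying a score forward is no error in itself; treating an untested child as unimpaired is.

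A third is that Protocol 3.1 allows specialist referral whenever data suggest delay. It does, but it requires neither a BSID-III nor a 24-month date, and it exempts children already under specialist care.

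Several stronger readings are tempting, and the documents do not support them:

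- A reader might infer that positive tests are thrown away. They are not. BSID-III results are summarised by visit in Tables 10.7 and 20.7 and appear in the listings.
- A reader might infer a breach of the rule "Medical input will override parent-reported data". That rule belongs to confirmation of Child Health Inventory reports. ASQ-3 and BSID-III have their own pathway, and a 24-month questionnaire does not contradict a 19-month test.
- A reader might infer that a test up to 3 months old cannot count as the 24-month result. The natural reading is that it can; the SAP simply does not say so.
- A reader might take any low BSID-III to be affected. A language-only deficit is outside the composite at every age.
- A reader might take the composite as the principal neurodevelopment result. Protocol Table 1 lists it among many endpoints.

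**Conclusion.** The point holds in this form. Without a 24-month BSID-III, a child with an earlier cognitive score <4 or motor composite <70 is, read literally, a 'no' on both BSID-III components, and unimpaired overall unless another component is positive.

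The number of such children cannot be derived from the documents, which give neither BSID-III positives nor retest rates, so no percentage lost should be quoted. The firm part is the weight of one child in the ARIOS Safety population: 2.0 points in retosiban, 2.3 in atosiban and 16.7 in placebo. If every earlier positive is retested at 24 months, the effect is zero.

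The undercount is one-directional within each arm. A reader might infer that it therefore always favours retosiban. It does not follow: a child lost from a comparator arm moves the difference the other way, and with 6 placebo infants by a large step. The study is descriptive, so no test or power statement is affected. The plan should still be changed, because the reported composite would otherwise mix two different states under one label.

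**What to change.** Analysis only; testing and referral stay as they are. In SAP 7.2.5:

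- **(a) Window.** State the age window within which a BSID-III counts as the 24-month result, and state that an existing result accepted in place of a repeat at the 24-month screen counts.
- **(b) No-event rule.** Do not apply 10.6.2 to the cognitive and motor components of a child with an earlier BSID-III below the cut-off and no later BSID-III. Show such children as 'earlier positive, not reassessed', separately from 'not impaired'.
- **(c) Two rows in Tables 10.9 and 20.9.** Give the composite once with 24-month results only, and once counting the most recent earlier BSID-III (9- or 18-month evaluation) where there is no 24-month one. A later score at or above the cut-off replaces an earlier low one.

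The cost is a paragraph of SAP text and a little programming on data already collected. For motor, the earlier composite has to be derived from the fine and gross motor scaled scores, as SAP 7.2.5 already does at 24 months. The downside is that the second row may count some children who caught up but were not retested, which is why both rows are shown.

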In May 2017, the corresponding treatment trials 200719 (NEWBORN-1, placebo comparison) and 200721 (ZINN, atosiban comparison) were terminated early due to poor recruitment and the length of time needed to complete the studies. The placebo-controlled trial enrolled only 23 of the target 900 participants over 17 months, and the atosiban comparator trial enrolled 97 of the target 330 participants over 29 months. Maternal, fetal, and neonatal adverse events were no more common with retosiban than placebo or atosiban. The development program was subsequently terminated with no further in utero exposure of retosiban planned.

PROTOCOL SUMMARY, Objectives

Primary

- To characterize the clinical safety in terms of infant and child morbidity and mortality in infants and children exposed to retosiban or comparator in utero
- To characterize the clinical safety in terms of neurodevelopment in infants and children exposed to retosiban or comparator in utero

Exploratory

- To characterize parental productivity loss related to a sick child and infant resource utilization in terms of hospital admissions, length of stay, emergency room/urgent care (ER/UC) visits, surgical procedures, and referral to specialty care or therapy visits for infants (up to age 2 years) exposed to retosiban or comparator in utero

PROTOCOL SUMMARY, Study Design

Infants and children will be followed at prespecified intervals until they have reached ~~5 years~~ 24 months chronological age.

The child's parent/legal guardian will be asked to complete a Child Health Inventory (CHI) at 2, 6, 9, 12, 15, 18, 21, and 24 months of the child's chronological ~~age and a modified CHI at 3, 4, and 5 years of the child's chronological age~~. The CHI questionnaire completed up to the 24-month time point will screen for infant mortality and morbidity and will capture data on resource utilization. ~~At the 3, 4, and 5 year time points, the CHI will screen for child mortality and morbidity, including any indicators of neurodevelopmental impairment.~~

During the ~~first~~ 24 months of participation in the study, if the parent/legal guardian indicates that the infant has been treated by specialists or has had ER/UC visits or hospitalizations, he/she will be asked to complete a productivity questionnaire to evaluate loss of parental productivity.

If at any of these time points a child has an M-CHAT-R/F score that indicates further evaluation is required and/or a CBCL/1.5–5 score ~~at or~~ above the 97th percentile for a subset of prespecified questions, the child will be referred to a specialist for a formal assessment.

PROTOCOL SUMMARY, Study Endpoints/Assessments

Study **primary** endpoints include the following and are further defined in Section 6.2.2:

Morbidity and mortality endpoints:

- Proportion of infants and children with newly diagnosed (after 28 days post EDD) chronic medical conditions by type of condition will be recorded and include the following:
 - Respiratory conditions
 - Neurological conditions
 - Sensory conditions
 - Gastrointestinal conditions
 - Cardiovascular conditions
 - Renal conditions
 - Growth parameters (~~only up to 24 months chronological age~~)
- Proportion of infants and children with newly diagnosed (after 28 days post EDD) congenital anomalies
- Proportion of infant and child deaths after 28 days post EDD and until ~~the end of the study~~**24 months chronological age**

Neurodevelopment endpoints:

- Proportion of infants with a BSID-III score >2 SDs below the mean score for the cognitive impairment (~~<70~~ **4**)
- Proportion of infants with BSID-III score >2 SDs below the mean score for the gross motor scale (~~<70~~ **4**)
- Proportion of infants with BSID-III score >2 SDs below the mean score for the fine motor scale (~~<70~~ **4**)

- Proportion of infants with a BSID-III score >2 SDs below the mean score for the language scale (~~<70~~ **70**)
- Proportion of infants with a CBCL/1.5–5 score ~~at or~~ above the 97th percentile for a subset of prespecified questions that relate to attention and hyperactivity problems
- Cognitive impairment: BSID-III Cognitive Scale Score of >2 SDs below mean score (~~<70~~ **4**) (at 24 months corrected age)
- Motor impairment: BSID-III Motor Composite Scale Score of >2 SDs below mean score (~~<70~~ **70**) (at 24 months corrected age)
- ~~Proportion of infants and children with at least 1 of the following indicators of neurodevelopmental impairment at the end of the study:~~
 - ~~Hearing impaired, uncorrected even with aids~~
 - ~~Blindness in 1 or both eyes or sees light only~~
 - ~~Cerebral palsy (moderate and severe)~~
 - Diagnosis of ASD, attention deficit disorder (ADD), or attention deficit hyperactivity disorder (ADHD)

Resource Exploratory resource utilization endpoints include:

- Number of hospital admissions, proportion of infants and children with any hospital admission, post-birth hospitalization discharge, by principal and secondary discharge diagnosis, type of hospital unit admitted to (e.g., neonatal intensive care unit [NICU], Pediatric, pediatric intensive care unit [PICU], Nursery level 3, intensive care unit [ICU]), and length of hospital stay per unit after 28 days post EDD and until ~~the end of the study~~ **24 months chronological age**.
- Combined length of hospital stay in days for all hospital admissions (for infants discharged from the delivery hospitalization and for babies who were never discharged home post-delivery) after 28 days post EDD and until ~~the end of the study~~ **24 months chronological age**.
- Number of surgical procedures (details of type and whether performed on an inpatient basis or at an outpatient/surgical center will be collected up to 24 months chronological age only) after 28 days post EDD and until ~~the end of the study~~ **24 months chronological age**.

Section 1.1, Background

Retosiban ~~is~~ was being developed for the treatment of spontaneous preterm labor (SPTL) in women with intact membranes.

Phase III SPTL treatment studies ~~will be~~ **were** conducted to demonstrate the ability of retosiban to prolong pregnancy and improve neonatal health, as well as to describe the maternal, fetal, and neonatal safety profiles. **The treatment studies were subsequently terminated due to limited recruitment and the development program was subsequently terminated with no further in-utero exposure planned.**

Section 1.1.1, Previous Human Experience

Study OTA105256 was the first Phase II clinical study of retosiban in preterm labor (n=93) [Thornton, 2015; GlaxoSmithKline Document Number CM2006/00201/0306].

~~The emerging safety profile for retosiban appears favorable. Results from protocol-specified maternal fetal and neonatal safety assessments were absent of any concerns and were similar between the retosiban and placebo groups. Furthermore, no clinically significant disparities in AEs were noted between groups [Thornton, 2015]. All reported AEs, whether maternal, fetal, or neonatal, were generally consistent with those reported in the Investigator's Brochure (IB) [GlaxoSmithKline Document Number CM2006/00201/03], IB Supplement 1 [GlaxoSmithKline Document Number 2015N228508_00], or in the study population.~~

